## 4.4. Extent of Exposure

The exposure data will be summarized through Week 16 and Week 36. The number and percentage of participants who receive study agent will be summarized by treatment group for the safety analysis set. Descriptive statistics will be presented for the following parameters:

- Number of administrations
- Cumulative total dose

In addition, the average exposure (number of administrations) and average duration of follow-up (weeks) will also be summarized by treatment group in the safety tables through different study time periods.

## 4.5. Protocol Deviations

In general, the following list of major protocol deviations may have the potential to impact participants' rights, safety or well-being, or the integrity and/or result of the clinical trial. Participants with major protocol deviations will be identified prior to database lock and will be summarized by category by treatment group through Week 16 and Week 36 for the FAS.

- Entered study and did not satisfy entry criteria
- Received wrong treatment or incorrect dose
- Received excluded concomitant or non-drug therapy
- Out of window visit
- Out of window procedure
- Other

A listing of participants with major protocol deviations and a listing of patients who missed scheduled study agent administration will also be provided by randomized treatment group. In addition, analyses of COVID-19 related protocol deviations will be provided.

## 4.6. Concomitant Medications

Concomitant medications for atopic dermatitis will be summarized by treatment group for the FAS. Prior medications are defined as any therapy used before the day of first dose (partial or complete) of study agent. Concomitant medications are defined as any therapy used on or after the same day as the first dose of study agent, including those that started before and continued after the first dose of study agent.

A list of participants who received a concomitant treatment that could improve AD will be provided.

## 5. EFFICACY

### 5.1. General Method of Analysis

Unless specified otherwise, efficacy data summaries will be provided by treatment group for the FAS. Statistical comparisons will be made between each of the bermekimab treatment groups (qw, q2w) and the placebo treatment group.

In general, for response efficacy endpoints, treatment comparisons will be performed using a Cochran-Mantel-Haenszel (CMH) test stratified by the baseline EASI severity (less severe  $EASI < 28$ , more severe  $EASI \geq 28$ ) or the Fisher's Exact test in case of rare events. For continuous efficacy endpoints, treatment comparisons will be performed using a Mixed-Effect Model Repeated Measure (MMRM) with treatment group, visit, baseline EASI severity (less severe, more severe) and baseline value for the efficacy endpoint as explanatory factors. The MMRM model will also include treatment group by visit interaction, baseline EASI severity by visit and baseline

value by visit interaction as additional explanatory factors. In addition, treatment differences and their associated 95% confidence intervals will be presented.

Descriptive statistics, such as mean, median, standard deviation, minimum and maximum, interquartile range for continuous variables, and counts and percentages for categorical variables will be used to summarize the data. Graphical data displays and subject listings may also be used to summarize the data.

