#### **10.5.3.2 Secondary Efficacy Analyses**

Secondary and exploratory efficacy endpoints will be summarized using descriptive statistics for continuous variables (n, mean, standard deviation, median, minimum and maximum value) and number and percentage for categorical variables.. The 95% CI of the mean change from baseline will be provided. The change from baseline in these endpoints at each week will be analyzed using a restricted maximum likelihood (REML)-based mixed model for repeated measures (MMRM) with fixed effects for treatment, week, stratification factor (baseline EASI severity), baseline score, baseline score by week interaction, and the treatment-by-week interaction, if applicable. The impact of the stratification factor will also be assessed. Categorical variables will be analyzed using CMH tests as used for the primary efficacy analysis. Full details will be provided in the SAP.

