**Summary of Amendment 1**

This amendment is to add additional statistical method of Fisher's Exact test for the binary efficacy endpoints in case of rare events. Originally, the planned analysis for treatment comparison in binary response endpoints is to use a Cochran-Mantel-Haenszel test.

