## **5.2. Analysis Specifications**

### **5.2.1. Level of Significance**

Unless otherwise specified, all statistical testing procedures will be performed at a 2-sided significance level of 0.05. Multiplicity adjustment was planned for the primary endpoint as specified in protocol Section 10.5.3 to maintain an overall Type I error of 0.05 or less for the primary endpoint analysis.

However, since this is a Phase 2 trial and stricter multiplicity adjustment for the primary endpoint at an overall alpha level of 0.05 is not required; a less stringent type I error control will be implemented instead. The study would be considered as positive if any of the comparisons for primary endpoint analysis (weekly injection group vs placebo, and every other week injection group vs placebo) is less than or equal to 0.05. Therefore, an overall Type I error rate will be maintained at 0.1 or less for the primary endpoint analysis. Nominal p-values will be reported for secondary analyses.

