### **5.3.4. Analysis Methods**

The primary endpoint will be compared between the each bermekimab group and the placebo group. The primary endpoint will be analyzed at Week 16 based on the composite estimand (Section 5.3.2) and the data from all participants in FAS (Section 2.4.1.1) will be analyzed according to randomized treatment group regardless of the treatment actually received.

In this primary analysis, the number and proportion of participants who achieve an EASI-75 at Week 16 will be summarized for each treatment group. To address the primary objective, a CMH chi-square statistic stratified by baseline EASI severity (less severe [EASI <28] or more severe [EASI ≥28]) at an alpha level of 0.05 will be used to compare each bermekimab group separately with placebo. The proportion difference between each bermekimab group and placebo group and its 2-sided 95% CI will be provided based on normal approximation with Mantel-Haenszel weights adjusting for baseline EASI severity.

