## **5.4. Secondary Efficacy Endpoints**

This section outlines the definition and analyses of these secondary endpoints related to NRS, EASI, IGA, DLQI, HADS, POEM, SCORAD, and GISS. Data from all participants in FAS will be included and analyzed according to the randomized treatment groups. For participants randomized to placebo, only participants who crossed over to receive bermekimab at Week 16 will be included in the efficacy summaries for the visits after Week 16. All statistical testing will be performed at the 2-sided 0.05 significance level. Nominal p-values will be presented.

Secondary efficacy endpoints will be summarized using descriptive statistics for continuous variables (n, mean, standard deviation, median, minimum and maximum value) and number and percentage for categorical variables. Continuous endpoints will be analyzed using a MMRM model to test the difference between treatment groups and adjust for missing data. The MMRM will include treatment, visit, baseline EASI severity, baseline score, baseline score by visit interaction, baseline EASI severity by visit interaction and the treatment-by-visit interaction, if applicable. The Least Square mean (LSmean) estimates and their corresponding 95% confidence interval (CI) will be provided at each time points. In addition, the estimates of LSmean difference and 95% CIs between treatment groups will be provided over time through Week 16 and p-values will be calculated at Week 16.

For the MMRM model, an unstructured covariance matrix for repeated measure within a participant will be used. In case that convergence cannot be achieved, autoregressive (1) covariance structure will be used.

For binary response endpoints, treatment comparisons will be performed using a Cochran-Mantel-Haenszel (CMH) test stratified by baseline EASI severity with missing data imputed with Non-Responder Imputation (NRI) defined in Section 5.2.2. In case of rare events, the Fisher's Exact test will be used for treatment comparisons in binary response endpoints.

Graphical data displays may also be used to summarize the over time data if applicable.

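### The rare-event fallback in SAP 5.1 and 5.4 is an unstratified Fisher's exact test with no definition of rare; an exact test stratified by baseline EASI severity would serve the same purpose and lose less power

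*SAP*

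**What the plan says.** SAP 5.1 sets the general rule for response endpoints: a CMH test stratified by baseline EASI severity, "or the Fisher's Exact test in case of rare events". SAP 5.4 repeats it for secondary endpoints: "In case of rare events, the Fisher's Exact test will be used for treatment comparisons in binary response endpoints". The SAP's summary of Amendment 1 gives the origin: "This amendment is to add additional statistical method of Fisher's Exact test for the binary efficacy endpoints in case of rare events".

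No section defines rare as a count, a rate or an expected cell size. None says whether it is judged by arm or pooled, or when. No strata are attached to Fisher's test. Randomisation is stratified by baseline EASI severity (Protocol 10.2, SAP 1.5.1).

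For the primary endpoint, SAP 5.3.4 names one test only: "a CMH chi-square statistic stratified by baseline EASI severity", which "will be used to compare each bermekimab group separately with placebo". Protocol 10.5.3.2 has no Fisher option for secondary endpoints either: "Categorical variables will be analyzed using CMH tests as used for the primary efficacy analysis". On error control, SAP 5.2.1 says that "all statistical testing procedures will be performed at a 2-sided significance level of 0.05", and also that "Nominal p-values will be reported for secondary analyses".

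**The concern.** There are two separate matters.

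1. **The test chosen.** Fisher's test in its usual form ignores strata. When responders are few, the analysis would therefore set aside the factor that the randomisation was built on, and use a very conservative test in a trial with about 30 patients per arm.
2. **The trigger.** With no number for rare, the same small counts can be analysed by either test within the SAP. Some sponsor staff are unblinded at the Week 16 database lock (SAP 1.5.2), so the decision should be fixed before then.

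At stake is how binary secondary endpoints with few responders are read, for example EASI-90, EASI-100 or IGA 0.

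**Working it through.** **Inputs from the documents.** About 90 patients at 1:1:1, so about 30 per arm (SAP 1.4, 1.5.1). Missing responses count as non-responders (SAP 5.2.2), so about 30 per arm stay in the analysis. For NRS, DLQI and HADS responder endpoints restricted by baseline score, the numbers would be smaller. Alpha is 0.05, two-sided.

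**Assumptions.** The documents give no rare-event rates, so all low rates below are mine. Strata are 15/15 per arm, with 18/12 as a check, and equal in both arms. CMH has no continuity correction.

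**The plan's own figure.** For 60% v 20%, n = [1.960 × √(2 × 0.4 × 0.6) + 0.842 × √(0.24 + 0.16)]² / 0.4² = (1.358 + 0.532)² / 0.16 = 22.3, so 23 per group, as stated. Power at 23 is 81.2%.

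**One table by hand: 5/30 v 0/30.**
- Fisher: 2 × C(30,5)/C(60,5) = 2 × 142,506/5,461,512 = 0.052.
- CMH, responders split 3 and 2 over the strata: observed minus expected = 5 − 2.5 = 2.5. The stratum variance is 15² × m × (30 − m)/(30² × 29), which is 0.698 for m = 3 and 0.483 for m = 2. The statistic is 6.25/1.181 = 5.29, p = 0.021. With all five in one stratum, p = 0.016.
- Exact stratified CMH: 0.054 for a 3/2 split, 0.0498 for 4/1 and 0.042 for 5/0.

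Other tables where the tests disagree: 4 v 0, Fisher 0.112 and CMH 0.035 to 0.042; 7 v 1, 0.052 and 0.015 to 0.025; 8 v 2, 0.080 and 0.022 to 0.041.

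**Is there a reason for an exact method?** With 4 responders in total, CMH rejects whenever all four fall in one arm. Under the null that has probability 2 × C(30,4)/C(60,4) = 2 × 27,405/487,635 = 11.2%. At 7 responders the figure is 10.3% and at 10 it is 8.0%. Averaged over totals, CMH's error is 0.3, 2.8, 5.4 and 5.0% at common rates of 2, 5, 10 and 20%, with a maximum of about 5.6% at 12%. Fisher's is 0.0, 0.15, 0.9 and 2.2% at the same four rates.

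**Power by full enumeration, 30 per arm, strata 15/15 (%).**

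| Placebo v active | CMH | Fisher | Exact stratified | Stratified mid-p |
|---|---|---|---|---|
| 3 v 20 | 60.8 | 34.1 | 37.8 | 49.4 |
| 5 v 20 | 45.4 | 24.1 | 26.6 | 36.7 |
| 5 v 25 | 63.4 | 43.6 | 45.7 | 57.2 |
| 5 v 30 | 78.0 | 63.1 | 64.5 | 74.5 |
| 10 v 30 | 50.3 | 37.2 | 37.8 | 48.0 |
| 20 v 60 (planning rates) | 90.5 | 85.1 | 85.2 | 90.3 |

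- CMH minus Fisher: 13 to 27 points in the first five rows and 5 at the planning rates. With no placebo responders and 15% active it is 67.8 − 28.9 = 39.
- Exact stratified minus Fisher: 0.6 to 3.7 points in the first five rows (35.1 − 28.9 = 6 at 0 v 15%). So most of Fisher's loss comes from exactness, and little from ignoring strata.
- Stratified mid-p minus Fisher: 11 to 15 points in the first five rows.

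**If severity is prognostic.** The rates below are for stratum 1/stratum 2; power is exact stratified v Fisher (%).

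| Active | Placebo | Strata 15/15 | Strata 18/12 |
|---|---|---|---|
| 20/10 | 5/1 | 19.7 v 14.5 | 19.4 v 16.4 |
| 30/10 | 5/1 | 43.0 v 33.9 | 46.4 v 40.4 |
| 25/15 | 5/0 | 43.2 v 37.1 | 41.8 v 38.4 |

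The gain is 3 to 9 points.

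**Direction of disagreement.** Over every table in both layouts, none had Fisher at or below 0.05 and CMH above it. None had Fisher at or below 0.05 and the exact stratified test above it.

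**The case against.** The strongest defence is that sparse counts are the ordinary reason for an exact test, and the conditional error of 10 to 11% shows that the amendment has a real purpose. This stands. It would be wrong to say that CMH has no type I error problem here.

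Three further points stand. SAP 5.4 words the switch as a rule and not as a choice between p-values. Secondary p-values are nominal, with no gatekeeping or success criterion, so 0.02 against 0.052 changes no formal decision. The study is powered only for EASI-75 at 60% v 20%, where responses are not rare.

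A reader might infer more than the documents support:

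- *That the open trigger inflates false positives.* It does not. Even taking the smaller of the two p-values gives CMH's own error, about 5.6% at most.
- *That the primary test is open to change.* Amendment 1 and SAP 5.1 are broadly worded, but 5.1 speaks in general terms and 5.3.4 specifies only CMH with a Mantel-Haenszel difference. The specific section governs. A sentence of confirmation is enough.
- *That the fallback was added after results were seen.* The text available does not date Amendment 1 relative to the Week 16 lock, so nothing can be said either way.
- *That the power loss is 13 to 27 points in general.* That range belongs to the assumed rates; across the rates tried the loss ran from 5 to 39.

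**Conclusion.** The point holds in a limited form. A small-sample fallback is justified; an unstratified Fisher test is not the best one, and its trigger is undefined. Fisher holds its error at 0 to 2% where 5% is allowed, and ignores the randomisation factor for no benefit. An exact test stratified by that factor keeps the same guarantee, lost none of Fisher's rejections at 0.05 in the layouts enumerated, and adds about 0 to 4 points of power, or 3 to 9 if severity is prognostic. It does not recover most of the gap to CMH, because that gap is the price of exactness.

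This rests on 30 per arm, equal stratum sizes in the two arms, assumed low response rates, and reading Fisher's test in its usual unstratified form. The consequence is lost power and avoidable ambiguity on nominal secondary analyses. It is not a threat to the primary conclusion.

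**What to change.** 1. In SAP 5.1 and 5.4, replace Fisher's test with the exact conditional CMH test stratified by baseline EASI severity. State the two-sided p-value definition (here: the probability of all active-arm totals at least as far from expectation as the one observed, given the stratum totals).
2. Define rare by a number of responders per endpoint and visit, counted blinded over all three arms and fixed before the Week 16 unblinding. A pooled count avoids looking at the arms.
3. State in 5.1 that the fallback does not apply to the primary endpoint, in line with 5.3.4.
4. Optionally report a stratified mid-p value as sensitivity. It should not be the main test: given the total, its error is 5.2% at 5 and at 8 responders and 8.0% at 10.

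The cost is a short SAP edit and a few lines of code. No data collection or sample size changes.

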## **5.2. Analysis Specifications**

### **5.2.1. Level of Significance**

Unless otherwise specified, all statistical testing procedures will be performed at a 2-sided significance level of 0.05. Multiplicity adjustment was planned for the primary endpoint as specified in protocol Section 10.5.3 to maintain an overall Type I error of 0.05 or less for the primary endpoint analysis.

However, since this is a Phase 2 trial and stricter multiplicity adjustment for the primary endpoint at an overall alpha level of 0.05 is not required; a less stringent type I error control will be implemented instead. The study would be considered as positive if any of the comparisons for primary endpoint analysis (weekly injection group vs placebo, and every other week injection group vs placebo) is less than or equal to 0.05. Therefore, an overall Type I error rate will be maintained at 0.1 or less for the primary endpoint analysis. Nominal p-values will be reported for secondary analyses.

### **5.2.2. Data Handling Rules**

No imputation will be performed for missing baseline values.

For the main analysis of primary endpoint of EASI-75 response at Week 16, a subject who discontinued treatment will be considered as a non-responder from that point onward. The remaining missing data will be imputed as non-responder. Supplementary analyses will be performed and include (1) using observed data regardless of whether the subject discontinued treatment or have missing data, and (2) data after treatment discontinuation will be considered as missing, missing response will be imputed by multiple imputation methods under the assumption of missing at random. Similar data handling rules (i.e., main analysis with non-responder imputation and 2 supplementary analyses) will also be applied for EASI-75 response over time through Week 16. The following data handling rules will be applied for other endpoints:

Binary secondary endpoints:

- Analyses will be similar to the main analysis of the primary endpoint. A subject who discontinued treatment will be considered as a non-responder from that point onward. The remaining missing data will be imputed as non-responder. Supplementary analyses will be performed for selected endpoint (i.e IGA responses) in the same manner as the primary endpoint.

Continuous secondary endpoints:

- If a subject discontinued treatment, zero will be assigned to improvement or percent improvement. Remaining missing data will not be imputed. A MMRM model will adjust for missing post baseline data and all available data from the 3 treatment groups through Week 16 or from Week 16 through Week 36 will be included. Under the assumption of missing at random (MAR), the missing data will be accounted for through correlation of repeated measures in the model. Supplementary analyses will be performed for selected endpoints (i.e. EASI total score, NRS itch score) and include (1) using observed data regardless of whether the subject discontinued treatment or have missing data, and (2) data after treatment discontinuation will be considered as missing, missing data will be addressed by MMRM model.

### 5.2.3. Treatment Groups

In the efficacy analyses, FAS will be used and the participants will be analyzed according to the randomized treatment groups they were assigned to, regardless of the treatments they actually received. Unless otherwise specified, efficacy analyses during each of study periods below are in general displayed as follows:

- Analysis through Week 16
  - Efficacy analyses for placebo comparison at Week 16 or through Week 16 will be summarized by randomized treatment group:
    - **Placebo:** Participants randomized to placebo group.
    - **Bermekimab 400 mg q2w:** Participants randomized to bermekimab 400 mg every other week injection group.
    - **Bermekimab 400 mg qw:** Participants randomized to bermekimab 400 mg weekly injection group.
    - **Combined Column:** Combined column which combines the data from the randomized and treated participants who are assigned to bermekimab 400 mg q2w or qw treatment groups.
- Analysis from Week 16 through Week 36
  - Efficacy data from Week 16 through Week 36 will be summarized by the following treatment groups:
    - **Placebo → Bermekimab 400 mg qw:** efficacy in participants randomized to placebo group.
      - ◆ Only placebo participants crossover to bermekimab 400 mg qw and received bermekimab at Week 16 will be included in the summary for the visits after Week 16.
    - **Bermekimab 400 mg q2w:** Participants randomized to bermekimab 400 mg every other week injection group.

- **Bermekimab 400 mg qw:** Participants randomized to bermekimab 400 mg weekly injection group.
- **Combined Column:** Combined column which combines the data from the randomized and treated participants who are assigned to bermekimab q2w or qw treatment groups at baseline.

These presentations allow assessment of efficacy over time between treatment groups.

### 5.3. Primary Efficacy Endpoint(s)

#### 5.3.1. Definition

The primary efficacy endpoint is the proportion of patients achieving an EASI-75 response at Week 16. The EASI is a validated measure used in clinical practice and clinical trials to assess the severity and extent of AD. Four AD disease characteristics will be assessed for severity by the investigator or designee on a scale of “0” (absent) through “3” (severe). In addition, the area of AD involvement will be assessed as a percentage by body area of head, trunk, arms, and legs and converted to a score of 0 to 6.

For each region, severity score is the sum of intensity for each of four signs.

- Severity score = Erythema + Edema/Papulation + Excoriation + lichenification intensity

For each region, multiple the severity score by the region score and by a multiplier. The multiplier is different for each body site.

- Head and neck: severity score x region score x 0.1
- Trunk: severity score x region score x 0.3
- Upper extremities: severity score x region score x 0.2
- Lower extremities: severity score x region score x 0.4

Add up the total scores for each region to determine the final EASI score. The minimum EASI score is 0 and the maximum EASI score is 72.

EASI-75 responder is defined as at least a 75% improvement from baseline in EASI total score.

#### 5.3.2. Estimands

##### Primary Estimand:

The **Composite Estimand** will be targeted for the primary endpoint. The Composite Estimand for the primary endpoint is defined by the following 5 attributes:

- Treatment:
  - Bermekimab 400mg q2w
  - Bermekimab 400mg qw

- Placebo

Note: treatment regimen includes protocol specified rescue therapy as needed.

- Population: Adult participants with chronic moderate to severe atopic dermatitis present for at least 3 years.
- Variable (Endpoint): EASI-75 binary responder variable at Week 16, where a subject who discontinues treatment is considered as non-responder after discontinuation.
- Intercurrent event: The intercurrent event of treatment discontinuation is addressed by the composite strategy, as reflected in the variable definition.
- Population-level summary: Difference in the proportions of subjects achieving EASI-75 response at Week 16 between the bermekimab and placebo treatment groups.

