#### **10.5.3.1 Primary Efficacy Analysis**

For the primary efficacy endpoint, the two bermekimab treatment groups will be compared with placebo. To account for these two comparisons, testing will be done in a sequential manner, each at the 0.05 alpha level. The bermekimab weekly injection group (Group 1) will be compared to the placebo group (Group 3) first. If this test is significant at the 0.05 level, then the bermekimab every other week injection group (Group 2) will be compared to the placebo group (Group 3). Otherwise, the P-value for Group 2 vs Group

3 will be considered nominal. This method to control the type-1 error will only be implemented for the primary efficacy analysis variable.

The number and percentage of patients with Eczema Area and Severity Index-75 (EASI-75) ( $\geq 75\%$  improvement from baseline) at week 16 will be presented by treatment group. Patients who terminate from the study early prior to week 16 will count as non-responders (non-achievers) in the primary efficacy analysis (Non-Responder Imputation). If a patient received rescue medication, the patient will be counted as a non-responder from the start of rescue medication. Additional treatment failure rules and sensitivity analyses will be discussed in the statistical analysis plan.

A Cochran-Mantel-Haenszel (CMH) general association test stratified by baseline EASI severity will be used to compare each bermekimab dose separately with placebo. The primary efficacy analysis population will be the mITT population.

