#### Supplementary Estimands for primary endpoint:

##### Supplementary Estimand 1

Same components as the primary estimand, except for the strategy used for treatment discontinuation.

**Hypothetical strategy:** assess the treatment effect as if the participants would not have discontinued treatment.

Note: Under this hypothetical strategy, EASI data collected after treatment discontinuation will not be used and will be set to missing in analysis.

##### Supplementary Estimand 2

Same components as the primary estimand, except for the strategy used for treatment discontinuation.

**Treatment policy strategy:** assess the treatment effect regardless of treatment discontinuation.

Note: Under the treatment policy strategy, EASI data collected after treatment discontinuation will also be used in analysis.

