### **5.3.3. Data Handling**

Participants who discontinued treatment prior to Week 16 will be considered EASI-75 non-responder at Week 16. In addition, participants with missing EASI evaluation at Week 16 will be considered as non-responders at Week 16.

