### **5.3.6. Subgroup Analysis**

For each of the subgroups defined in Section 2.5, the difference between each of the bermekimab treatment group and placebo group in the proportion of participants achieving EASI-75 at Week 16 and its 95% confidence interval (when the number of participants permits) will be calculated. Subgroup analyses will not be stratified by baseline EASI severity.

In addition, the proportion of participants achieving EASI-75 at Week 16 by investigator site will be summarized. The same data handling rules specified in Section 5.2.2 will apply for subgroup analysis.

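### The SAP's primary estimand counts rescued patients on their observed EASI-75 response, reversing without explanation the protocol's rule that they are non-responders, and no planned analysis applies the protocol rule

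*SAP*

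**What the plan says.** **Protocol.** Section 10.5.3.1, on the primary analysis, states: "If a patient received rescue medication, the patient will be counted as a non-responder from the start of rescue medication". It then leaves further detail to the SAP: "Additional treatment failure rules and sensitivity analyses will be discussed in the statistical analysis plan". Section 2.10 allows topical corticosteroids or calcineurin inhibitors for AD rescue and lets study treatment continue when they are used. Section 2.11 asks investigators to keep first-line rescue topical where possible.

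**SAP.** The treatment attribute of the primary estimand (5.3.2) carries the note "Note: treatment regimen includes protocol specified rescue therapy as needed". The only intercurrent event named is treatment discontinuation, handled by the composite strategy. Data handling follows suit. In 5.2.2, "a subject who discontinued treatment will be considered as a non-responder from that point onward", and remaining missing data count as non-response. In 5.3.3, "Participants who discontinued treatment prior to Week 16 will be considered EASI-75 non-responder at Week 16", and a missing Week 16 EASI is also non-response. Rescue appears in neither section.

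**Other planned analyses of the endpoint.** Both supplementary estimands are described as "Same components as the primary estimand, except for the strategy used for treatment discontinuation". For subgroups, "The same data handling rules specified in Section 5.2.2 will apply for subgroup analysis". The per-protocol analysis (5.3.7) uses the 5.3.3 rules on a set (2.4.1.2) that does not exclude rescued patients.

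**Reporting of co-medication.** SAP 4.6 plans a by-arm summary of concomitant AD medications and a list of participants given treatment that could improve AD. SAP 4.5 summarizes major deviations by arm, including excluded concomitant therapy, through Week 16 and Week 36.

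**The concern.** The two governing documents give different answers to the question of who is a primary responder. The patients affected are foreseeable: topical rescue is the preferred first step, and because study drug may continue, the SAP's discontinuation rule does not catch them.

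The protocol does not delegate this choice. What it hands to the SAP is failure rules in addition to the rescue rule. Nor is the change signalled. SAP 5.2.1 states and explains its departure from the protocol on type I error, and Amendment 1 concerns Fisher's exact test only; neither mentions rescue.

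At stake is a primary result that can take two values from the same data, with only one of them planned for reporting. Some sponsor staff are unblinded at the Week 16 lock (SAP 1.5.2), so a conflict still open at that point would have to be settled after results are known to some of those involved.

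**Working it through.** **1. The same patient under each document.** Topical rescue before Week 16, still on study drug, EASI-75 met at Week 16:

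| Source | Status |
|---|---|
| Protocol 10.5.3.1 | Non-responder |
| SAP primary (5.3.2, 5.2.2, 5.3.3) | Responder |
| Supplementary 1, hypothetical | Responder; only data after discontinuation are set to missing |
| Supplementary 2, treatment policy | Responder; observed data used |
| Subgroups (5.3.6) | Responder; 5.2.2 rules |
| Per-protocol (5.3.7) | Responder if in the set; 5.3.3 rules |

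No row of the SAP reproduces the protocol's classification.

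**2. The plan's own figure.** Inputs from protocol 10.1: 60% vs 20%, two-sided 0.05, about 80% power, Pearson chi-square. With the pooled-null normal approximation,

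n = [1.960·√(2·0.4·0.6) + 0.842·√(0.6·0.4 + 0.2·0.8)]² / 0.4² = 22.3, so 23 per arm and 69 in total.

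This reproduces the stated size (power 81% at 23 per arm). With about 90 randomized 1:1:1, or 30 per arm,

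power = Φ{[0.4·√30 − 1.960·√(2·0.4·0.6)] / √0.40} = Φ(1.317) = 91%.

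The sample size is not in dispute.

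**3. Size per patient.** 1/30 = 3.3 percentage points. Unstratified Pearson p-values at 30 per arm, active vs placebo responders:

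| Responders | p |
|---|---|
| 14 vs 6 | 0.028 |
| 14 vs 7 (one placebo patient reclassified) | 0.058 |
| 15 vs 7 (one in each arm) | 0.032 |
| 18 vs 6 (the planned 60% vs 20%) | 0.0016 |
| 18 vs 10 (four placebo patients) | 0.038 |
| 18 vs 11 (five placebo patients) | 0.071 |

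A borderline result can turn on one patient in one arm. A result at the planned rates needs five, all on placebo.

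**4. Power, illustration only.** All rescue rates here are assumed. Taking 60/20 as protocol-rule rates, the SAP-rule rate = protocol-rule rate + (fraction rescued × response among the rescued). At 30 per arm:

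| Rescue: placebo, active; response if rescued | SAP-rule rates | Power |
|---|---|---|
| None | 60% vs 20% | 91% |
| Rare: 10%, 5%; 25% | 61.25% vs 22.5% | 88% |
| Balanced: 20%, 20%; 40% | 68% vs 28% | 89% |
| Heavier on placebo: 20%, 10%; 50% | 65% vs 30% | 79% |
| Extreme on placebo: 50%, 10%; 50% | 65% vs 45% | 34% |
| Heavier on active: 10%, 20%; 50% | 70% vs 25% | 96% |

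Neither document says which rule the 60/20 assumption reflects. If these are SAP-rule rates, nothing is lost against plan. The protocol rule would then subtract the same product: rescue of 30% on placebo and 10% on active with 30% responding gives 57% vs 11% (power 98%); 10% and 20% with 50% responding gives 50% vs 15% (power 84%).

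**The case against.** The best defence is that including rescue in the regimen is a recognised treatment-policy type of choice, made openly in the estimand. Protocol section 10 calls itself a general description and leaves specifics to the SAP. The study is Phase 2, and if rescue is heavier on placebo the SAP rule is the conservative one. Much of this stands: the SAP's choice is defensible in itself, and keeping it is one of the two acceptable fixes. But leaving details to the SAP does not cover reversing an explicit rule for the primary endpoint without saying so.

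Several stronger readings are tempting and are not supported:

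- *The SAP leaves rescue undefined.* The note in 5.3.2 is itself a rule: observed response counts. The fault is an unexplained reversal.
- *Rescue will be invisible.* SAP 4.6 and 4.5 plan by-arm summaries that will show part of it. They define no rescue flag and leave responder status unchanged.
- *The SAP rule favours bermekimab, or costs the trial its power.* More rescue on placebo shrinks the difference and enough more on active widens it. The 34% figure needs half of placebo patients rescued and half of those responding, which nothing in the documents supports.
- *The secondary endpoints contradict the protocol too.* Protocol 10.5.3.2 says "Categorical variables will be analyzed using CMH tests as used for the primary efficacy analysis", which carries over the test and not the rescue rule.
- *Systemic rescue is misclassified as well.* Protocol 2.10 exempts systemic agents required for AD rescue, yet lists the same agents for study drug discontinuation through week 16. Until those statements are reconciled, one cannot say whether the SAP's discontinuation rule catches these patients. The finding does not need them.

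**Conclusion.** The concern holds for the primary endpoint and must be fixed. The protocol and SAP classify the same topically rescued patient differently, the SAP does not acknowledge the change, and no planned analysis gives the protocol's result. This conclusion rests on the text alone.

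The firm figure for size is 3.3 points per reclassified patient in a 30-patient arm. The aggregate effect is unknown in both size and direction because no rescue rates are given. On assumed rates, power changes little with rare or balanced rescue (88–89% against 91%), falls if placebo rescue is heavy, and rises to 96% in the scenario with more rescue on active. These powers use a normal approximation, and the p-values an unstratified test in place of the planned stratified CMH. They illustrate the point; the severity does not depend on them.

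**What to change.** Before the Week 16 lock, reconcile SAP 5.3.2, 5.2.2 and 5.3.3 with protocol 10.5.3.1. Either option removes the contradiction:

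1. Add rescue as a second intercurrent event under the composite strategy (non-response from its start), delete the note in 5.3.2, and keep the analysis that ignores rescue as supplementary.
2. Keep the SAP estimand, state and justify the departure from the protocol, and add an analysis of the primary endpoint with rescue as non-response.

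In both cases, define a rescue flag from the concomitant-medication data and use it to add a Week 16 cut of rescue use to the by-arm summary already planned in SAP 4.6. If the lock has already taken place, which the documents do not say, report the added analysis as specified after unblinding. Applying the same rule to binary secondary endpoints would serve consistency; it would not restore a protocol rule.

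Separately, the statements on systemic agents within protocol 2.10 should be reconciled.

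**Cost.** SAP wording, one table, and a written rescue definition or a blinded review, since protocol 2.11 leaves rescue to investigator discretion. Under the protocol rule, each arm's response rate falls by the share of patients rescued and still responding.
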